3.2 Secondary Aims and Endpoints

Aim 3: To determine whether tranexamic acid leads to a decrease in the incidence of WHO Grade 2 or higher bleeding events

Endpoint: Proportion of patients with WHO Grade 2 or higher bleeding events daily following activation of study drug or placebo

Aim 4: To determine whether tranexamic acid leads to a reduction in the number of days with any grade bleeding event

Endpoint: Proportion of patients with any grade bleeding event following activation of study drug

Aim 5: To determine whether tranexamic acid leads to a decrease in the highest observed grade of bleeding (as measured on WHO bleeding scale) during the study period

Endpoint: Highest grade of bleeding (as measured on WHO bleeding scale) during study period in each enrolled patient

Aim 6: To determine whether tranexamic acid leads to a reduction in the number of red blood cell or platelet transfusions required

Endpoint: Number of red blood cell or platelet transfusions per patient daily following activation of study drug

Aim 7: To determine whether tranexamic acid prolongs the amount of time from activation of study drug to the first episode of WHO Grade 2 or higher bleeding

Endpoint: Length of time from activation of study drug to first episode of WHO Grade 2 or higher bleeding

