4.2 Exclusion Criteria

To be eligible for participation in the study, potential subjects must not meet any of the following criteria:

- Diagnosis of acute promyelocytic leukemia
- History of ITP, TTP or HUS
- History of inherited or acquired bleeding disorder
- History of inherited or acquired prothrombotic disorder
- Diagnosis of DIC
- Patient must not have WHO Grade 2 bleeding or greater within 48 hours prior to enrollment or study drug activation
- Patient must not have received PEG-Asparaginase within the 7 day period prior to enrollment. If this product is given within the 8-14 day period prior to enrollment patients are eligible if PT, PTT, INR and fibrinogen are obtained and are within 1.5 times the upper limits of normal.
- Patient must not be receiving tranexamic acid or other anti-fibrinolytic agent or any other agent to promote hemostasis (which includes DDAVP, recombinant Factor VII, Prothrombin Complex Concentrate, Estrogen Derivatives and Progestins)
- Patient must not be receiving therapy with anticoagulation or antiplatelet therapy (which includes heparin infusion, enoxaparin, aspirin. If anticoagulant/antiplatelet therapy is discontinued when platelet count is <50,000/uL patient will be eligible for enrollment)
- Patient must not be receiving platelet growth factors
- Patient has a current/prior history of thromboembolic event within the past six months. If history of thromboembolic event the patient should be >30 days from completion of anticoagulation therapy
- Patient has a current/prior history of sinusoidal obstruction disease
- Patient has visible blood in their urine
- Patient with renal dysfunction (defined in Section 6, Table 2), hemodialysis or with anuria (defined as <10mL urine/hour over 24 hours)
- History of seizures
- Allergy to tranexamic acid
- Pregnancy
- Unwilling to accept blood transfusions
- Requires platelet transfusion threshold higher than study protocol (If the patient is enrolled on study and begins treatment with either the study drug or placebo, and subsequently requires a platelet transfusion threshold greater than the study protocol they will remain on study).

5. Trial Enrollment

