5.2 Randomization

This trial is designed as a prospective, randomized, controlled, blinded (patient, caregiver, physician, assessor) trial with two parallel groups and a primary endpoint of feasibility and safety. Randomization will be performed as block randomization with a 1:1 allocation within blocks of size four.

When a consented participant's platelet count falls to $\leq 50,000/\mu\text{L}$ and the platelet count is expected to continue to fall and remain $\leq 20,000/\mu\text{L}$ for 5 days or longer, the patient will be randomized to either the tranexamic acid arm or the placebo arm by the investigational pharmacy. When the randomized subject's platelet count is $\leq 30,000/\mu\text{L}$ with an expectation that the platelet count will be $\leq 20,000/\mu\text{L}$ for 5 days or longer the study drug will be activated. Activation of the study drug will act as time point zero for all study endpoints.

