8.4 Day 1 of Study Drug

- Hemostatic/Bleeding Assessment
 - If participant has had Grade 2 or higher bleeding within 48H of initiation of the study drug this should not be activated. They will be eligible for activation of the study drug later if bleeding later resolves.

- Thrombotic Assessment (via chart review)
- Laboratory Assessment (to be drawn prior to first dose of study drug)
 - CBC
 - Serum Creatinine
 - Urinalysis (if >72 hours from last Urinalysis)
 - Fibrinolysis study labs
- Data on Platelet Transfusions
 - Number of platelets transfused
 - Source of platelet transfusions (apheresis or whole blood)
 - HLA or cross-match compatible
 - Reason for transfusion
- Data on Red Blood Cell Transfusions
 - Number of units transfused
 - Reason for transfusion
- Adverse Event Assessment and Reporting – All Grade 3 or greater adverse events will be documented and followed
- Medication Review – Document new or discontinued medications

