11.3 Analysis Populations

Participants will be analyzed according to the groups to which they were initially randomized: tranexamic acid or placebo. All efficacy analysis will be by an Intent to Treat strategy. Participants will be included in the analysis if they received one or more dose of the study drug, even if participant discontinued participation, cross over between treatment groups or received prophylactic transfusions at a threshold higher than that prescribed in the protocol.

Efficacy analysis on patients will include data gathered on patients from the time of activation of the study drug until discharge or until a point 30 days following activation of the study drug, whichever time point occurs sooner. Any participants who have been consented to participate within the study and randomized to a treatment group but did not meet criteria to begin treatment with the study drug (whether due to development of

exclusion criteria or due to platelet count remaining >30,000/uL) and did not receive any doses of the study drug will not be included in the efficacy analysis.

The population of patients used for analysis of safety will be all patients who receive one or more dose of the study drug. Follow-up for mortality and for thrombotic events will occur at 7 days (+/- 3 days) and 30 days (+/- 3 days) post activation. Adverse events and Serious Adverse events will be based on clinical diagnosis obtained from review of the medical record and by patient report during the surveillance period. Patients will be assessed by daily visits and medical chart reviews by the investigator or study staff during the study period. Patients will be assessed by in-hospital visit (if in patient), clinic visit or telephone (if outpatient) during follow-up period after cessation of the study drug.

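### Aim 4's any-grade bleeding proportion does not separate Grade 1 bleeding ongoing at the first dose from new bleeding, which weakens the comparison; Aim 5 is touched only at the Grade 0/1 boundary

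*Combined protocol and SAP*

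**What the plan says.** **Who may start.** Section 4.2 (Exclusion Criteria) states "Patient must not have WHO Grade 2 bleeding or greater within 48 hours prior to enrollment or study drug activation". Section 8.4 repeats the check on Day 1: "If participant has had Grade 2 or higher bleeding within 48H of initiation of the study drug this should not be activated". The only other current-bleeding bar in 4.2 is "Patient has visible blood in their urine". Other Grade 1 bleeding does not prevent activation.

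**What is counted.** In 3.2, Aim 4 is "To determine whether tranexamic acid leads to a reduction in the number of days with any grade bleeding event", but its endpoint is the patient-level "Proportion of patients with any grade bleeding event following activation of study drug". Section 11.1.2 repeats that proportion. The Aim 5 endpoint is "Highest grade of bleeding (as measured on WHO bleeding scale) during study period in each enrolled patient".

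**From when.** Section 5.2 states "Activation of the study drug will act as time point zero for all study endpoints". Section 11.3 agrees: "Efficacy analysis on patients will include data gathered on patients from the time of activation of the study drug until discharge", or until 30 days after activation if that is sooner. It leaves out randomized patients who were never dosed.

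**What is collected.** Bleeding is scored on the day of randomization (8.3), on Day 1 (8.4) and on Days 2-30 (8.5).

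**How it is analysed.** Section 11.5 names a method for Grade 2 or higher bleeding. It names none for any-grade bleeding or highest grade, and no section uses a baseline bleeding grade.

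**The concern.** For Aims 3 and 7 the outcome is Grade 2 or higher bleeding, and the activation rule keeps out patients who had bleeding of that grade in the previous 48 hours. Aim 4 uses a lower outcome threshold, and neither an entry rule nor a baseline rule matches it. Study drug starts at platelet counts of 30,000/uL or below (5.2), where some Grade 1 bleeding at the first dose is plausible. If it is seen again on Day 2, the patient has any-grade bleeding after activation, whichever arm they are in. A preventive treatment cannot prevent the onset of a bleed that is already there.

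The plan handles fibrinolysis differently: a pre-dose sample is the defined baseline (8.7). Bleeding has no such reference, although the assessment that could supply it is scheduled.

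What is at stake is the bleeding signal. The synopsis hopes for a signal of effectiveness. A diluted any-grade difference would be a poor guide for the larger trial, and an undefined event leaves the counting rule to be settled after the data are seen.

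**Working it through.** **The plan's own figure.** There is no power calculation to reproduce. The 20 participants in 11.7 are a feasibility target, and 5.3 puts 10 activated patients in each arm.

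**Inputs.**
- From the documents: 10 per arm; Grade 1 bleeding allowed at activation; any grade counts afterwards.
- Assumed, because the documents give no value: p, the share of patients with Grade 1 bleeding that continues past the first dose, and the rate of new bleeding among the others (70% control, 40% tranexamic acid).
- Also assumed: everyone with ongoing bleeding is counted as an event in both arms.

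**Dilution of the Aim 4 proportion.** Observed proportion = p + (1-p) × r, where r is the new-bleeding rate. The arm difference is then (1-p) × (r_control - r_treated).

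| p | Control | Tranexamic acid | Difference |
|---|---|---|---|
| 0 | 70% | 40% | 30 points |
| 20% | 0.2 + 0.8×0.7 = 76% | 0.2 + 0.8×0.4 = 52% | 24 points |
| 40% | 0.4 + 0.6×0.7 = 82% | 0.4 + 0.6×0.4 = 64% | 18 points |
| 60% | 0.6 + 0.4×0.7 = 88% | 0.6 + 0.4×0.4 = 76% | 12 points |

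**Other assumed rates.** With new bleeding of 88% v 44%, the difference falls from 44 points to 35.2 at p = 20% and 22.0 at p = 50%. The number per arm for 80% power (two-sided 0.05) rises from 17 to 24 and 45. The 88% is borrowed from the background section, which does not state a grade, so this too is only an illustration.

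**Chance imbalance.** Suppose one arm has three more patients with ongoing Grade 1 bleeding than it would otherwise have had. Each raises the count only if that patient would not have bled anyway. The arm's proportion moves by 3/10 × (1-0.7) = 9 points at the control rate, or 3/10 × (1-0.4) = 18 points at the treated rate. With independent binomial counts at 10 per arm, the arms differ by three or more such patients with probability 16% at p = 20% and 25% at p = 40%. For two or more, the probabilities are 39% and 49%.

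**Aim 5.** Ongoing Grade 1 bleeding turns a highest grade of 0 into 1 and changes nothing above that. Take an assumed distribution over grades 0/1/2/3+ of 12/38/40/10% (control) and 40/35/20/5% (treated). The probability of a better grade on treatment, counting ties as half, is 0.68 at p = 0, 0.67 at p = 20% and 0.65 at p = 50%. Grade 2 or higher stays at 50% v 25% throughout.

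**The case against.** **The text is silent; it does not direct that baseline bleeding be counted.** A reader might infer that bleeding from before the first dose is generally an outcome. The documents do not support that. Activation is time zero (5.2) and the efficacy window opens there (11.3), so a bleed that resolved beforehand is outside it. Only bleeding that continues past the first dose is unaddressed. Section 8.9 also refers to an appendix on scoring by organ system that is not in the text available here. It might hold further counting rules.

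**Aim 4 asks about days.** On that scale, continued days of an existing bleed are a fair outcome that treatment might shorten. This stands. The dilution belongs to the patient-level proportion, which does not match the aim, and continuing bleeding should not be dropped from a count of days.

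**Aim 5's wording.** A reader might take its study period to include the assessment on the day of randomization. No section says so, and 5.2 and 11.3 point to activation. The wording is loose and needs aligning, no more.

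**Pre-dose timing on Day 1.** In 8.4 the instruction to act before the first dose is attached to laboratory samples. The bleeding assessment decides activation, which implies that it comes first, but the plan does not say so.

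**The study is not powered for bleeding.** Sections 2 and 11.7 concede this, and 11.5 allows further analyses at completion. That limits the severity. It does not remove the reason to fix the definition beforehand, since 11.7 looks to this trial to help plan the next one.

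**Conclusion.** The point holds for the Aim 4 proportion and is minor. As written, the endpoint does not distinguish ongoing from new Grade 1 bleeding, and a literal reading multiplies the risk difference by (1-p). Under assumed rates of 70% v 40%, 30 points become 24 to 12 as p runs from 20% to 60%. Neither p nor an any-grade effect is in the documents, so those sizes are illustrations. They are upper bounds on the loss if some patients with ongoing bleeding stop bleeding before they are next assessed.

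Three stronger conclusions are tempting and not supported:
- **Bias between arms.** The rule applies equally to both randomized arms. The result is lost sensitivity plus possible chance imbalance.
- **A 30-point swing from three extra patients.** That requires that none of the three would have bled later. Under the assumed rates the shift is 9 to 18 points.
- **Comparable damage to Aim 5.** Only its Grade 0/1 boundary is affected; differences at Grade 2 or higher are untouched.

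**What to change.** Change the wording in 3.2, 11.1.2 and 11.5, with a matching line in 8.4:

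- State that the Day 1 bleeding assessment is made before the first dose, and that its WHO grade and site are the baseline.
- Report the Day 1 grade by arm.
- For the Aim 4 proportion, report bleeding that is new in site or higher in grade than baseline, alongside the all-bleeding count.
- Keep continuing bleeding in any summary of days with bleeding, since that is what Aim 4 asks about.
- For Aim 5, count from activation in the population defined in 11.3. Show highest grade by Day 1 grade (0 v 1), descriptively or with a simple adjustment.

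The activation rules need no change for this. The cost is small: the assessment is already scheduled and no visit is added. The drawbacks are fewer events in the new-or-worsened count and small subgroups by Day 1 grade at 10 per arm, so those tables should be read as descriptive.

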3.3 Safety Endpoints

Adverse events and serious adverse events will be monitored and collected from the time of activation of the study drug until a period up to and including 30 days after the last dose of the study drug. Adverse events and serious adverse events will to be assessed by CTCAE v.4.0 criteria and compared between study drug and placebo arms. The following events will specifically be compared across study arms;

- Incidence of thrombotic events (A thrombotic event is defined as venous or arterial thrombosis confirmed on imaging study, which may include Doppler US, CT scan, MRI or venography)
- Incidence of veno-occlusive disease (also known as sinusoidal obstruction syndrome)
- All cause-mortality, including incidence of death due to thrombosis

4. Population

Pediatric patients with hematologic malignancy or solid tumors receiving chemotherapy or undergoing BMT.

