6.3 Stopping Points

The patient's physician or the principal investigator may withdraw the patient from the study for any reason. An End of Study form will be completed with the reason for withdrawal documented in such an occurrence.

The study drug will be permanently discontinued in one of the following circumstances:

- The participant meets an exclusion criteria (either newly developed or not recognized previously) that precludes further study participation
- The patient has been on study drug or received placebo medication for 30 days from the date of study drug activation
- The patient's platelet count increases spontaneously from $<30,000/\mu\text{L}$ to $\geq 50,000/\mu\text{L}$ across two successive platelet measurements with no intervening platelet transfusion
- The patient's platelet count remains $\geq 30,000/\mu\text{L}$ on 2 measurements made at least 46 hours apart without intervening platelet count of $<30,000/\mu\text{L}$ or a decrease in platelet of greater than 50% between two measurements and without intervening platelet transfusion
- The patient is prescribed any other procoagulant, antiplatelet or anticoagulant agent by their treating physician (this includes open label tranexamic acid)
- The patient is discharged from hospital admission
- The patient experiences a thrombotic event
- The patient develops sinusoidal obstructive disease
- The patient develops visible hematuria, renal dysfunction (as defined in Section 6, table 2) or anuria
- The patient has a recurrent incident of complete central line occlusion: defined as the inability to access or infuse through a central line requiring instillation of fibrinolytic agent such as alteplase for clearing. This does not include lines that require certain patient positioning for instillation of agents, which suggest a "kink" in the line. A recurrent incident is when the definition is met on 2 separate occasions while receiving study drug.
- The patient becomes pregnant

If any of the above reasons lead to cessation of the study drug it should not be restarted even if the patient later meets criteria again for the study drug.

Subjects have the right to withdraw consent at any time. If a patient withdraws their consent for further participation, the subject will be asked to grant consent for the study

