6.4 Temporary Stopping Points

The study drug will be temporarily discontinued in the following situations:

- Diagnosis of DIC by the treating team or treating physician
- First event of central line occlusion (as defined above)

In these situations, as detailed above, the study drug may be restarted after resolution of the situation.

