8.10 Thrombotic Assessment

Assessment for thrombotic event will be performed via a review of medical chart notes and relevant imaging studies obtained within the time period from prior assessment.

9. Adverse Event Reporting

Whenever possible investigators should report adverse events as diseases or syndromes instead of reporting individual components of symptoms, signs, laboratory abnormalities or sequelae.

This study will be using the descriptive terminology developed by the National Cancer Institute for use in reporting adverse events: Common Toxicology Criteria for adverse events (CTCAE) version 4.03. These criteria can be found at: https://evs.nci.nih.gov/ftp1/CTCAE/CTCAE_4.03/CTCAE_4.03_2010-06-14_QuickReference_5x7.pdf. All Grade 3 or higher adverse events will be documented.

The CTCAE grading scale is applied to each adverse event term. Grades were developed using the following guidelines:

- Grade 1:** Mild; asymptomatic or mild symptoms; clinical or diagnostic observations only; intervention not indicated.
- Grade 2:** Minimal, local or non-invasive intervention indicated; limiting age-appropriate ADL.
- Grade 3:** Medically significant but not immediately life-threatening; hospitalization or prolongation of hospitalization indicated; disabling; limiting self-care ADL.
- Grade 4:** Life-threatening consequences; urgent intervention indicated.
- Grade 5:** Death related to AE.

The definitions that will be applied to adverse events recorded in this trial are given below:

Adverse event means any untoward medical occurrence associated with the use of a drug in humans, whether or not considered drug related.

Life-threatening adverse event or life-threatening suspected adverse reaction. An adverse event or suspected adverse reaction is considered “life-threatening” if, in the view of either the investigator or sponsor, its occurrence places the patient or subject at immediate risk of death. It does not include an adverse event or suspected adverse reaction that, had it occurred in a more severe form, might have caused death.

Serious adverse event or serious suspected adverse reaction. An adverse event or suspected adverse reaction is considered “serious” if, in the view of either the investigator or sponsor, it results in any of the following outcomes: Death, a life-threatening adverse event, inpatient hospitalization or prolongation of existing

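### Complete central line occlusion stops study drug but is not a named between-arm safety comparison, and a low-grade, unimaged occlusion may reach none

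*Combined protocol and SAP*

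**What the plan says.** **Thrombosis endpoint (3.3).** "A thrombotic event is defined as venous or arterial thrombosis confirmed on imaging study, which may include Doppler US, CT scan, MRI or venography". This is one of three events singled out for comparison across arms; the other two are veno-occlusive disease and all-cause mortality.

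**Permanent stop (6.3).** "The patient has a recurrent incident of complete central line occlusion: defined as the inability to access or infuse through a central line", with a fibrinolytic such as alteplase needed to clear it. Lines that work only in certain patient positions are excluded. On recurrence: "A recurrent incident is when the definition is met on 2 separate occasions while receiving study drug". A separate item in the same list reads "The patient experiences a thrombotic event".

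**Temporary stop (6.4).** The listed trigger is "First event of central line occlusion (as defined above"). Study drug may be restarted after resolution.

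**Thrombotic assessment (8.10).** "Assessment for thrombotic event will be performed via a review of medical chart notes and relevant imaging studies". It has no line-occlusion item.

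**General adverse events.** 3.3 also states: "Adverse events and serious adverse events will to be assessed by CTCAE v.4.0 criteria and compared between study drug and placebo arms". On what is collected, Section 9 says: "All Grade 3 or higher adverse events will be documented"; 8.4 to 8.6 repeat that threshold. Section 13.1 adds serious events whatever their attribution, and events of any grade that are both unexpected and at least possibly related to study drug.

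**The concern.** The protocol treats complete line occlusion as important enough to interrupt and then end treatment, but does not list it among the safety events to be compared. Tranexamic acid inhibits fibrinolysis, and the occlusion definition turns on needing a fibrinolytic to clear the line. Section 2 describes thromboembolism as a major concern with this drug class, safety is a primary aim (3.1), and Section 11.7 says the trial is meant to establish safety ahead of a larger efficacy trial.

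If occlusions were unevenly distributed between arms, the planned tables might not show it. The thrombosis row could read zero in both arms while treatment stops for occlusion differed, and whoever plans the next trial would lose information that staff had already gathered at the bedside.

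**Working it through.** The plan states no figure on this point, so the check is to trace each route by which an occlusion could reach a by-arm comparison.

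| Route | Source | Condition for an occlusion to enter |
|---|---|---|
| Thrombosis endpoint | 3.3 | Imaging confirms a thrombosis |
| General AE comparison | 3.3, 8.4–8.6, 9 | Grade 3 or higher |
| SAE comparison | 3.3, 9, 13.1 | Meets a seriousness criterion |
| All-grade collection | 13.1 | Unexpected and at least possibly related |
| Named comparison | 3.3 | None: not listed |

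The 6.3 definition satisfies none of these conditions by itself. It requires no imaging, assigns no grade, and is listed apart from a thrombotic event. Section 9's generic Grade 2 description covers local or non-invasive intervention, which could plausibly fit a line cleared by instillation. The CTCAE grading for the specific term is not in the documents, so I do not rely on it. What remains uncovered is an occlusion that is unimaged, below Grade 3, non-serious, and judged either expected or unrelated.

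**What a by-arm row could show.** Inputs: 10 activated subjects per arm (5.3); two-sided 0.05 level and 95% intervals (11.5).

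- *Upper limit for 0/10 (exact, two-sided 95%):* 1 − 0.025^(1/10) = 0.308, or 30.8%.
- *Fisher's exact test, all events in one arm.* With k events in total, the two-sided p is 2 × C(10,k)/C(20,k).
  - k = 4: 2 × 210/4845 = 0.087.
  - k = 5: 2 × 252/15504 = 0.033.
  - So p<0.05 starts at 5 versus 0.
- *Chance of at least one affected patient in an arm of 10*, 1 − (1 − p)^10, for assumed per-patient rates (the documents give none):
  - 1%: 9.6%
  - 2%: 18.3%
  - 5%: 40.1%
  - 10%: 65.1%
  - 20%: 89.3%

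An empty row would therefore exclude little, and a formal test would detect only an extreme split. The row's value is descriptive.

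**The case against.** The strongest reply is that the existing safety net is wider than the three named events.

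- **General comparison.** 3.3 compares adverse and serious adverse events by arm, and the three named events are additional. A reader might infer that occlusions never enter the safety comparison. The documents do not support that: those that are Grade 3 or higher, or serious, do enter.
- **All-grade route.** Line occlusion is not among the expected events in 9.4, and a possible relation under 9.2 needs only a compatible sequence of events. Many occlusions could therefore qualify under 13.1. But this depends on case-by-case judgement: 9.4 does list thromboembolic events, so an occlusion might be called expected, and the 13.1 list sits under the serious-event heading.
- **DSMB.** A reader might infer that the DSMB could not see occlusions. Section 12.2 gives it access to all data, split by masked arm, and lets it request more. Its listed review items do not name thrombosis either. What stands is only that nothing ensures an occlusion table is prepared.
- **Raw data.** Daily medication review should often show the fibrinolytic, and chart notes are reviewed daily. That makes the data recoverable, but it is not a planned comparison.
- **Primary conclusion.** A reader might infer that the primary safety conclusion would be falsely reassuring. The primary safety endpoint is adverse events, serious adverse events and death (3.1, 11.1.1), not the thrombosis count.
- **Meaning and frequency.** Nor do the documents say that every occlusion is a clot, or that occlusions are commoner than imaged thrombosis. They give no reason for the stopping rule and no rate for either event.

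An imaging-based thrombosis definition is specific and defensible, and nothing here argues for changing it. These replies narrow the point considerably but do not close the residual gap.

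**Conclusion.** The point holds in limited form. Complete central line occlusion drives temporary and then permanent stopping of study drug, yet it is not a named comparison. Unless it is imaging-confirmed, Grade 3 or higher, serious, or both unexpected and at least possibly related, no stated route takes it into a between-arm table. A patient with two such occlusions and no imaging-confirmed thrombosis would stop drug permanently and contribute zero to the thrombosis row.

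The size of the gap cannot be given, because it depends on the occlusion rate and on how staff grade and attribute the events; the documents fix neither. It is a shortfall in planned safety reporting and does not invalidate the primary endpoint. It is worth correcting because it concerns a risk the protocol itself singles out and the events must already be identified in order to apply 6.3 and 6.4.

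**What to change.** Leave the stopping rules and the imaging-based thrombosis definition as they are.

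1. Add complete central line occlusion, as already defined in 6.3, to the 3.3 list of events compared across arms.
2. Record every occurrence after activation of study drug, whatever its CTCAE grade, seriousness or attribution. The daily thrombotic assessment is a natural place for the item.
3. Report by arm the number of patients with at least one occlusion, the number of events, and the temporary and permanent stops that resulted. Patients with at least one is the count to read first, because the stopping rule limits how many events a patient can accrue on drug.
4. Keep this in a row separate from imaging-confirmed thrombosis, include it in the DSMB tables, and label it descriptive.

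**Cost.** One case report form line and one table row. Some counted occlusions will not be thrombotic, since 6.3 excludes only position-dependent lines; the separate row keeps them from being read as thrombosis.
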